According to researchers, patients with cancer have a higher risk of developing a second new cancer when compared to people without cancer. In clinical studies of newly diagnosed multiple myeloma, a higher number of second cancers were reported in patients treated with lenalidomide as induction therapy (treatment for several cycles to reduce number of cancer cells) and/or bone marrow transplant followed by lenalidomide for a long period of time compared to patients treated with induction therapy and/or bone marrow transplant then placebo (a capsule containing no lenalidomide). Patients should make their doctors aware of their medical history and any concerns they may have regarding their own increased risk of other cancers.

Complete and updated adverse events are available in the Investigational Drug Brochure and the IND Safety Letters.

1.4 **Lenalidomide and Immune Reconstitution:**

Lenalidomide is an immunomodulatory drug that is FDA approved for the treatment of multiple myeloma and myelodysplasia. Lenalidomide also has clinical activity in a number of other hematologic malignancies, including CLL.¹⁷⁻²⁰ In CLL, lenalidomide is thought to mediate its anti-tumor activity through modulation of the tumor microenvironment rather than a direct cytotoxic effect on the leukemic cells.^{19,21,22} Immunomodulatory mechanisms include disrupting pro-tumor cytokines, anti-angiogenic signaling and activation of adaptive humoral and T-cell immunity.^{19,21,22} Notably, both *in vitro* and *in vivo* data suggest that oral lenalidomide can repair defects in the T-cell immune synapse and reduce T regulatory levels in patients with CLL. In addition, there are reports that serum immunoglobulin levels can be enhanced with exposure to lenalidomide.

Notably, previous studies in patients with multiple myeloma also suggest that lenalidomide may improve the immune response to pneumococcal vaccination.²³ A “window of opportunity” study evaluated the immune response in patients with multiple myeloma receiving lenalidomide treatment. The first cohort received an initial dose of the pneumococcal 7-valent conjugate vaccine (PCV) prior to the initiation of lenalidomide and a second vaccination while on lenalidomide. The second cohort received both vaccinations while on lenalidomide. The PCV-specific humoral and cellular responses were greater in the second cohort suggesting lenalidomide augmented the vaccine response of these patients.²³

1.5 **Strategic Concept:**

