Immunity following pneumococcal disease is directed primarily against the capsular polysaccharide of the bacteria serotype involved. Antibody mediated killing of *Streptococcus pneumoniae* by phagocytes is an important mechanism of protection. The two most common serologic methods for quantifying and evaluating the function of antibodies induced by pneumococcal vaccination are IgG quantification by enzyme-linked immunosorbent assay (ELISA) and measurement of opsonophagocytic activity (OPA) of antibodies from sera of vaccinated individuals. The OPA assay is a functional antibody assay that is important for the evaluation of candidate vaccines and is a requirement for the licensure of new pneumococcal conjugate vaccine formulations. OPA reflects *in vivo* mechanisms of defense against pneumococcal infection. **The measurement of functional antibodies has been shown to better correlate with protection in infant populations and it is also likely to be a better indicator for elderly populations than the measurement of antibodies specific to the capsular polysaccharides by ELISA assay.**²⁷ While there is no defined correlate of protection for pneumococcal vaccines, it is thought that OPA titers are associated with protection against invasive pneumococcal disease. The primary endpoint for Prevnar 13® adult clinical trials that led to the FDA approval of Prevnar 13® relied on immunogenicity endpoints of OPA geometric mean ratio (GMT) and proportion achieving at least 4-fold increase in OPA titer.²⁸ Nevertheless, even when assessing OPA titers, most vaccine trials also measure and report quantitative IgG antibodies specific to *Streptococcus pneumoniae* serotypes.

- We will report pre-vaccination (baseline) and Day 28 post-vaccination OPA GMTs for each serotype (4, 9V, 23F) in vaccine group and vaccine group + lenalidomide.

- We will report pre-vaccination (baseline) and Day 28 post-vaccination *Streptococcus pneumoniae* serotype specific IgG GMTs for each serotype (1, 3, 4, 5, 6B, 7F, 9V, 14, 18C, 19F, 19A, and 23) in vaccine group and vaccine group + lenalidomide.
- Correlative endpoints for vaccine immunogenicity will include comparison of fold change in OPA GMT for each serotype (4, 9V, 23F) between vaccine group and vaccine + lenalidomide group and comparison of fold change in *Streptococcus pneumoniae* quantitative IgG level for each serotype (1, 3, 4, 5, 6B, 7F, 9V, 14, 18C, 19F, 19A, and 23) between vaccine group and vaccine + lenalidomide group.

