16.0 Statistical Considerations and Methodology

16.1 Overview:

This is a randomized Phase II study designed to compare the response rate of the control arm (Pevnar 13 alone) to the experimental arm (Pevnar 13 plus lenalidomide).

16.11 Primary Endpoint:

The primary endpoint of this trial is the rate of response to the Pevnar 13 vaccine, which will be compared between the two arms. A response will be defined as a four-fold rise from pre-vaccine (day 15) to 28 days after immunization (day 43) for ≥ 2 of the 3 serotypes studied by opsonophagocytic activity (OPA) of antibodies from sera. Throughout Section 16.0, response will be considered synonymous with “success”, unless specified otherwise. All patients meeting the eligibility criteria who have signed a consent form and, received the Pevnar 13 vaccine will be evaluable for response, with the exception of patients who are determined to be a major treatment violation or flag.

16.2 Statistical Design:

16.21 Decision Rule:

It has been shown that CLL patients have poor response to vaccines. In previous studies, responses to the polysaccharide pneumococcal vaccine (Pneumovax) have been remarkably low, with responses ranging from 10-22%.^{13,14} Similar responses are expected with the Pevnar 13 vaccine. The addition of lenalidomide is expected to increase response rates to Pevnar 13 vaccine.

A randomized trial comparing the experimental arm (Pevnar 13 plus lenalidomide) against the control arm (Pevnar 13 alone) will be conducted as described by Rubinstein³⁴. We will enter 26 evaluable patients on each arm of the study using a 1:1 randomization scheme utilizing the Pocock and Simon dynamic allocation procedure³⁵, where patients are stratified based on age (<65 vs. ≥ 65), Rai stage (MBL or 0 vs. I), and previous Pneumovax (yes vs. no). A sample size of 26 patients per arm provides 80% power to detect an improvement in response rate from 10% to 30%, using a one-sided test at a significance level of 0.16 (EAST 6.2).

The z-score will be calculated for testing the null hypothesis that the difference of response rates between the two arms is equal to zero, based on the normal approximation with pooled variance of standardized test statistics.

16.211 Final Decision Rule: The final analysis will take place after all 52 evaluable patients have completed the response evaluation at 43 days.

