16.3 Analysis Plan: The analysis for this trial will commence at planned time points (see 16.2) and at the time the patients have become evaluable for the primary endpoint. Such a decision will be made by the Statistician and Study Chair, in accord with CCS Standard Operating Procedures, availability of data for secondary endpoints (eg, laboratory correlates), and the level of data maturity. It is anticipated that the earliest date in which

the results will be made available via manuscript, abstract, or presentation format is when last patient has been followed for at least 2 months.

16.31 Primary Endpoint:

16.311 Definition: The primary endpoint of this trial is the rate of response to the Prevnar 13 vaccine, which will be compared between the two arms. A response will be defined as a four-fold rise from pre-vaccine (day 15) to 28 days after immunization (day 43) for ≥ 2 of the 3 serotypes studied by opsonophagocytic activity (OPA) of antibodies from sera. Patients who are not evaluated for the OPA titers at both pre-vaccine (day 15) and day 43 due to a missed blood draw or other reasons will be considered a non-responder. All patients meeting the eligibility criteria who have signed a consent form and received the Prevnar 13 vaccine will be evaluable for response, with the exception of patients who are determined to be a major treatment violation or flagr.

16.312 Estimation: The proportion of successes will be estimated in each arm by the number of successes divided by the total number of evaluable patients. Ninety-five percent confidence intervals for the true success proportion will be calculated in each arm based on the normal approximation. Comparison of response rates between the two treatment groups will be performed using a one-sided z-test (based on normal approximation with pooled variance of standardized test statistics) at significance level 0.16.

16.32 Secondary Endpoints:

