16.321 Disease status by physical exam and complete blood counts will be evaluated in each patient. For CLL, each patient will be classified as CCR, CCRi, PR, SD, or PD per Section 11.2 at the time of the 6 week assessment of immune response. The distribution of disease status will be evaluated in each arm and will be summarized descriptively. Patients will be classified as responders (CCR, CCRi, PR) vs. non-responders (SD, PD). For MBL, patients will be classified as Not PD vs. PD. Differences in disease status response will be compared between the two arms using Fisher's exact test.

16.322 Time to treatment for progressive CLL will be defined as the time from the date of registration to the date of initiation of treatment for progressive CLL. The distribution of time to treatment will be estimated in each arm using the method of Kaplan-Meier. Time to treatment will be compared between the two arms using log-rank statistics.

16.323 Adverse Events: All eligible patients that have initiated treatment will be considered evaluable for assessing adverse event rate(s). Platelets and hemoglobin will be graded according to the Grading Scale for Hematologic Adverse Events in CLL Studies in Appendix IV. The maximum grade for each type of adverse event will be recorded for each patient, and frequency tables will be reviewed for each arm to determine

patterns. Additionally, the relationship of the adverse event(s) to the study treatment will be taken into consideration.

16.33 Correlative Analyses:

16.331 Pre-vaccination (day 15) and day 28 post-vaccination OPA GMTs for each serotype (4, 9V, 23F) will be reported in the vaccine and vaccine + lenalidomide groups. The fold-change in OPA GMT from baseline to 28 days post-vaccination will be evaluated for each serotype, where two-sample t-tests will be used to compare GMTs between the vaccine and vaccine + lenalidomide groups.

16.332 Pre-vaccination (day 15) and day 28 post-vaccination *Streptococcus pneumoniae* serotype specific IgG GMTs for each serotype (1, 3, 4, 5, 6B, 7F, 9V, 14, 18C, 19F, 19A, and 23) will be reported in the vaccine and vaccine + lenalidomide groups. The fold-change in quantitative IgG GMT from pre-vaccine (day 15) to 28 days post-vaccination will be evaluated for each serotype, where two-sample t-tests will be used to compare GMTs between the vaccine and vaccine + lenalidomide groups.

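### The Day 15 reference titre follows about 14 days of lenalidomide in Arm A only, no analysis checks whether it has shifted since registration, and Section 16.331 names the reference inconsistently

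*Combined protocol and SAP*

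**What the plan says.** **Primary endpoint.** Section 16.311 defines response as a "four-fold rise from pre-vaccine (day 15) to 28 days after immunization (day 43") in at least two of the three serotypes. Sections 2.11, 11.1 and 16.11 use the same reference. A patient without OPA titres at both times counts as a non-responder.

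**Exposure before the reference sample.** Section 7.1 gives Arm A lenalidomide on days 1-14 and both arms the vaccine on day 15. Arm B receives no lenalidomide. Section 1.4 states that "there are reports that serum immunoglobulin levels can be enhanced with exposure to lenalidomide".

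**OPA fold change.** The first sentence of 16.331 reports titres at pre-vaccination, day 15. The second reads: "The fold-change in OPA GMT from baseline to 28 days post-vaccination will be evaluated for each serotype". Objective 2.31, for the same quantity, and 16.332, for IgG, both use Day 15. Section 14.22 says "We will report pre-vaccination (baseline) and Day 28 post-vaccination OPA GMTs". Section 16.333 uses baseline for the start of the study.

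**Samples.** Footnote 5 of Section 4.0 and the table in 14.1 list Baseline, Day 15 and Day 43 as separate draws, with red-top serum for OPA mandatory at each. Section 18.1 lists OPA titres among the initial forms. The kit sheet in Appendix VI calls for red-top tubes at Baseline and Day 43 only.

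**What is absent.** No section compares the Day 15 titre with the registration titre, or classifies response from the registration serum.

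**The concern.** The reference for the primary endpoint is measured after randomisation and, in one arm only, after exposure to the drug under test. If lenalidomide moved the OPA titre before vaccination, a four-fold rise from Day 15 would become harder to reach in Arm A (after an upward shift) or easier (after a downward one). Objective 2.11 asks about the whole six-week course, but any change in its first two weeks goes into the reference, where no planned analysis would show it. The recommendation for further testing rests on a single comparison of response rates, so a reader of the result would want to know that the reference was comparable between arms.

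The wording adds a smaller problem. Baseline and Day 15 are different draws, so a programmer following 16.331 literally could compute a fold change that objective 2.31 does not describe.

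**Working it through.** **1. The plan's own power.** Inputs from 16.21: 26 evaluable per arm, 10% versus 30%, "using a one-sided test at a significance level of 0.16", with a z-test "based on the normal approximation with pooled variance of standardized test statistics".

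- Critical value: z(0.84) = 0.9945. Section 16.211 states 0.988; at 26 per arm both cut-offs give the same exact power.
- Null SE = sqrt(2 x 0.20 x 0.80 / 26) = 0.1109. Alternative SE = sqrt((0.10 x 0.90 + 0.30 x 0.70) / 26) = 0.1074.
- Power = Phi((0.20 - 0.9945 x 0.1109) / 0.1074) = Phi(0.835) = 0.798. The stated 80% is reproduced.
- Exact binomial enumeration of the same rule gives 0.82 at 10% versus 30%, and a 0.19 chance of success at 10% versus 10%. These are the comparators below.

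**2. Exposure.** Doses on days 1-14 precede the Day 15 draw. The window of 3 days either side makes this 11 to 17 days, if Day 1 is the first dose.

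**3. What a drift would do.** The documents give neither a drift nor an SD, so both are assumptions. Take one serotype, a normal log2 fold rise with SD 1.5-2.5, and a 30% response in Arm A measured from registration serum. Let the Day 15 titre in Arm A be r times the registration titre, with the Day 43 titre unchanged. The Day 15-referenced response is then

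p = 1 - Phi(z + log2(r)/SD), with z = 0.5244 for 30%.

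Example: r = 1.25, SD 1.5: 0.5244 + 0.3219/1.5 = 0.739, so p = 0.230. Exact power against a 10% control is 0.64.

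| Arm A drift r | Day 15 response in Arm A | Exact power |
|---|---|---|
| 1.0 | 30% | 0.82 |
| 1.1 | 27-28% | 0.75-0.78 |
| 1.25 | 23-26% | 0.64-0.72 |
| 1.5 | 18-22% | 0.46-0.62 |

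The actual two-of-three rule, simulated with between-serotype correlation 0.3-0.6 and SD 1.5-3, gives 0.58-0.73 at 1.25-fold and 0.36-0.63 at 1.5-fold. The one-serotype simplification therefore does not exaggerate the effect.

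In the other direction, suppose r = 0.8 and 10% response in both arms from registration serum. The one-serotype model then raises the chance of declaring success from 0.19 to 0.27-0.33. Nothing in the documents suggests such a fall; it is shown only because the direction is unknown.

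**4. Reference wording, side by side.** The first sentence of 16.331, objective 2.31 and 16.332 say Day 15. The second sentence of 16.331 says baseline. Section 14.22 treats baseline as a synonym for pre-vaccination, whereas 4.0, 14.1 and 16.333 treat it as the start of the study.

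**5. The kit sheet.** If Appendix VI is followed, there is no Day 15 serum and 16.311 scores the patient as a non-responder. With a share m of Day 15 sera missing in both arms, the rates become 0.10(1-m) and 0.30(1-m):

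- m = 20%: 8% versus 24%, exact power 0.75.
- m = 50%: 5% versus 15%, exact power 0.64.

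**The case against.** The strongest reply is that the primary endpoint contains no error. The question is response to vaccination, a titre drawn at the time of vaccination isolates it, and four sections agree on Day 15. That stands, and the reference should not change.

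A reader might infer that lenalidomide is known to raise the Day 15 titre and so biases the result. The documents do not support this. Section 1.4 speaks of serum immunoglobulin levels in general, with no dose, duration or size, and not of serotype-specific OPA. No section says what two weeks at the starting dose does to OPA. If a rise did occur, it would work against Arm A and make a positive result conservative.

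A reader might also infer from the table that the trial has less than its stated power. It does not follow: the 10% and 30% are rates for the response as the protocol defines it, from Day 15. The table places the 30% on a registration reference in order to show sensitivity.

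Nor does 16.331 show that a second reference was intended. Its own first sentence, objective 2.31 and 14.22 make loose wording the likeliest explanation, and the analysis is correlative.

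Finally, registration-referenced response is not a clean arbiter. It credits any pre-vaccine drug effect to Arm A and so answers a different question. That is right, and it limits how the supportive analysis may be read.

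What the reply does not answer is that comparability of the reference between arms is assumed, although serum to examine it is collected.

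**Conclusion.** The point holds as a gap in the planned analyses and an inconsistency in wording, not as a fault in the primary definition. Three things are established from the text: the Day 15 titre is drug-exposed in Arm A only; no comparison with registration is planned; and 16.331 conflicts with 2.31 and 16.332 over the reference for the OPA fold change.

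The size is conditional. Under the assumptions in the working, a 1.1-fold drift costs little (exact power 0.75-0.78 against 0.82) and a 1.5-fold drift costs a great deal (0.46-0.62). Whether there is any drift is unknown, and that is the reason to measure it. The sample size and the stated 80% power stand.

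The kit-sheet conflict is more concrete, because a missing Day 15 serum turns directly into a non-response. The change is worth making, but it does not bear on the validity of the design.

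**What to change.** 1. Keep Day 15 as the primary reference.
2. In 16.331, replace *from baseline* by *from pre-vaccine (day 15)*. In 14.22, replace *(baseline)* by *(day 15)*.
3. Add to 16.31 a between-arm comparison, by serotype, of the change in OPA titre from registration to Day 15. Arm B shows what happens without the drug.
4. Add to 16.31 one supportive analysis that classifies response from the registration serum. State in advance that it describes the combined effect of drug and vaccine and does not correct or overrule the primary result.
5. Reconcile the red-top schedule in Appendix VI with Section 4.0 and the table in 14.1, both of which require Day 15 serum.

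Cost: protocol and SAP wording and a little more analysis. If registration serum was not already going to be assayed, there is also one more OPA run per patient. Section 11.1 names only the Day 15 and Day 43 titres, but the table in 14.1 and the initial forms in 18.1 suggest that the registration assay was intended. Sample size, endpoint and decision rule do not change.

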4.0 Test Schedule

Tests & Procedures	Active Monitoring Phase				
	Days Prior to Registration	Day 15 (+/- 3 days)	Day 28 (+/- 7 days)	Day 43 (+/- 4 days)	Observation: 28 days after end of first cycle (Day 72 +/- 10 days)
	≤14 days				
Medical history	X				
Adverse event assessment	X	X		X	X
Physical exam, including PS, weight and vital signs	X			X	X
Height	X				
Register in the REVLIMID REMS® program (Arm A only)	X ⁸				
Counseling for the REVLIMID REMS® program (Arm A only)			X		
Tumor measurement by physical exam	X ¹			X ¹	
Peripheral blood immunophenotyping by flow cytometry	X ²				
CBC with differential and reticulocytes	X	X		X	X
Serum pregnancy test	X ³	X ³	X ³	X ³	
Chemistry group (SGOT [AST], SGPT [ALT], total bilirubin, serum creatinine, calcium, alkaline phosphatase, uric acid, LDH, potassium)	X	X		X	
Glucose	X				
Direct bilirubin	X ⁷				
CD38	X ²				
ZAP-70	X ²				
IGHV	X ⁴				
CD49d	X ⁴				
Serum protein electrophoresis	X			X	
Beta-2-microglobulin	X				
Peripheral blood CLL FISH panel	X ⁶				
Serum quantitative immunoglobulins (IgG, IgA, IgM)	X			X	
Coombs test (monospecific direct coombs IgG and C3)	X				
EKG	X				
Quantitative T & B cells, peripheral blood	X			X	

Prevna 13 pneumococcal vaccination		X			
Research blood specimens (see Section 14.0)	X ^{5,R}	X ^{5,R}		X ^{5,R}	

1. Physical exam should measure the spleen and liver noting the maximal distance below the respective costal margins and should record the bidimensional diameter of the largest palpable node in each area of involvement including the following sites: left neck (sub-mandibular, cervical, supra-clavicular), right neck (sub-mandibular, cervical, supra-clavicular), left axillary, right axillary, left groin (inguinal, femoral) and right groin (inguinal, femoral).
 2. May be waived for patients who have previously had full flow immunophenotyping consistent with CLL performed at Mayo Clinic. Similarly, if the patient has previously had CD38 and/or ZAP-70 testing performed at Mayo Clinic, repeat assay is elective after discussing with the study chair.
 3. For women of childbearing potential only. Must follow pregnancy testing requirements as outlined in the Revlimid REMS® program material.
 4. If patient has previously had done clinically at Mayo Clinic, this does not need to be repeated.
 5. Blood specimens will be collected and submitted at baseline, Day 15 and Day 43. Kits are required.

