The response rates will be compared between the two arms using EAST6. If the response rate is higher in the experimental arm, where the z-score is greater than 0.988 (p-value < 0.162), this will be considered sufficient evidence that the experimental arm may be recommended for further testing in subsequent studies. Otherwise, we will conclude that there is not statistical evidence of superiority of the experimental regimen.

16.212 Over Accrual: If more than the target number of patients are accrued, the additional patients will not be used to evaluate the stopping rule or used in any decision making process. Analyses involving over accrued patients are discussed in Section 16.33.

16.22 Sample Size:

The randomized phase II study design to be used is fully described in section 16.21. A maximum of 52 evaluable patients (26 in each arm) will be accrued onto this phase II study unless undue toxicity is encountered. We anticipate accruing an additional 6 patients (3 in each arm) to account for ineligibility, cancellation, major treatment violation, or failure to receive the Prevnar 13vaccine. Maximum projected accrual is 58 patients.

16.23 Accrual Rate and Study Duration:

The anticipated accrual rate is approximately 3-4 patients per month. Therefore, the accrual period for this phase II study is expected to be about 1.5 years. The final analysis can begin approximately 1.75 years after the trial begins, i.e. as soon as the final patient accrued to this trial has completed the response evaluation at 43 days and data entry has been completed.

16.24 Power and Significance Level: Assuming that the responses are binomially distributed in each arm, the operating characteristics of the current design can be tabulated according to various true differences of the proportions, including the probabilities that the experimental regimen is superior to the control regimen.

If the true difference is proportions is	0	0.10	0.20	0.30
Then the probability of declaring that the experimental regimen warrants further studies is....	0.16	0.51	0.80	0.95

16.25 Other Considerations: Toxicity, quality/duration of response, and patterns of treatment failure observed in this study, as well as scientific discoveries or changes in standard care will be taken into account in any decision to terminate the study.

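### Scoring a missing Day 15 titre as vaccine failure is not reliably conservative for the between-arm difference, the mandatory baseline serum goes unused as a check, and the kit sheet omits the Day 15 serum

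*Combined protocol and SAP*

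**What the plan says.** The primary response is a four-fold OPA rise from Day 15 to Day 43 in at least 2 of 3 serotypes. Sections 2.11, 11.1, 16.11 and 16.311 all anchor it to Day 15.

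Section 16.311 covers any evaluable patient "not evaluated for the OPA titers at both pre-vaccine (day 15) and day 43 due to a missed blood draw or other reasons". A patient without the titres "due to a missed blood draw or other reasons will be considered a non-responder". Section 16.312 estimates each rate as "the number of successes divided by the total number of evaluable patients", so these patients stay in the denominator.

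A second pre-vaccine serum exists by design. Section 4.0, footnote 5, says: "Blood specimens will be collected and submitted at baseline, Day 15 and Day 43. Kits are required". The table in Section 14.1 marks the serum for the OPA and IgG assays as mandatory at all three times. Section 7.1 gives the vaccine on Day 15, so the baseline serum is pre-vaccine in both arms. Section 14.22 itself equates pre-vaccination with baseline when it describes the OPA summaries.

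The kit instructions in Appendix VI differ. They call for the heparin tubes at every time point, but for the red-top serum tubes only at Baseline and Day 43.

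The plan gives no expected rate of missing titres, and no missing-data sensitivity analysis for the primary endpoint.

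**The concern.** A lost tube or failed assay becomes a vaccine failure in the endpoint that drives the recommendation for further testing. For a single-arm rate, scoring missing as failure can only lower the estimate. For a difference between two arms it can push either way, depending on which arm loses more titres. Arm B receives the vaccine only, with no placebo (Section 7.1), so equal losses cannot be taken for granted.

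Part of the problem can be examined with material already in hand. A patient with usable baseline and Day 43 sera has a measurable rise across vaccination, yet the rule records no response. The kit sheet gives Day 15 loss a concrete route. The allowance of 6 extra patients in Section 16.22 does not list missing titres among its reasons, and such patients remain evaluable, so they are not replaced.

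**Working it through.** **Inputs.** From Section 16.21: 26 evaluable patients per arm, 10% against 30%, one-sided 0.16, and an expected response of 10–22%. From Section 16.211: go if the pooled z exceeds 0.988. Missing fractions m are assumed, and missingness is taken as unrelated to response.

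**1. The plan's own power.** Φ{[√n(pE − pC) − zα√(2p̄(1 − p̄))] / √(pC(1 − pC) + pE(1 − pE))}, with p̄ = 0.20 and zα = 0.9945. This is (√26 × 0.20 − 0.9945 × √0.32) / √0.30 = (1.0198 − 0.5626) / 0.5477 = 0.835, and Φ(0.835) = 0.798. The stated 80% reproduces. Exact enumeration of z > 0.988 over all 27 × 27 outcomes gives 0.821. The exact go probability with equal true rates is 0.168 at 22% and 0.192 at 10%, so shifts are measured from those values and not from 0.16.

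**2. Equal loss, 10% against 30%.** Missing-as-failure turns each rate p into p(1 − m).

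| m in each arm | Rates tested | Exact power under the rule | Exact power, complete cases |
|---|---|---|---|
| 0 | 10% v 30% | 0.821 | 0.821 (26 per arm) |
| 5% | 9.5% v 28.5% | 0.807 | not run |
| 10% | 9% v 27% | 0.791 | 0.789 (23 per arm) |
| 15% | 8.5% v 25.5% | 0.773 | 0.783 (22 per arm) |

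The complete-case sizes are 26 × 0.90 = 23.4 and 26 × 0.85 = 22.1, rounded. At 10% missing, dropping the patients costs as much as failing them. With both true rates at 22%, 10% loss in each arm moves the go probability only from 0.168 to 0.172.

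**3. Unequal loss, both true rates 22%.**

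| Missing in A / B | Rates tested A / B | Exact go probability |
|---|---|---|
| 0 / 0 | 22% / 22% | 0.168 |
| 5% / 15% | 20.9% / 18.7% | 0.227 |
| 15% / 5% | 18.7% / 20.9% | 0.127 |

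The scoring creates a difference of 0.22 × (0.95 − 0.85) = 2.2 percentage points where none exists. With a wider assumed split, 20% missing in one arm and none in the other, the probability is 0.291 (loss in B) or 0.090 (loss in A).

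**4. One patient.** z = [(e − c)/26] / √(2p̄(1 − p̄)/26).
- 5 responders in Arm A and 3 in Arm B: p̄ = 8/52, z = 0.0769/0.1001 = 0.77, no go.
- 5 and 2: p̄ = 7/52, z = 0.1154/0.0947 = 1.22, go.

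One Arm B responder with a lost tube is enough to change the verdict.

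**5. Severity of a worst-case bound.** Count missing Arm B titres as responses and missing Arm A titres as failures. At 10% missing per arm under 10% against 30%, the Arm B rate is 0.10 × 0.90 + 0.10 = 0.19 and the Arm A rate is 0.30 × 0.90 = 0.27. The exact go probability falls to 0.39.

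**6. Serum schedule side by side.** Section 4.0 and Section 14.1: baseline, Day 15, Day 43. Appendix VI: Baseline and Day 43. Section 14.31 requires kits at sites outside Rochester, and a site that follows the kit sheet would have no Day 15 OPA serum. If losing either titre counts, each of its patients would be a non-responder.

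**The case against.** The rule is prespecified, identical in both arms, and keeps every evaluable patient, which suits a phase II screen. Day 15 is the vaccination visit, so an evaluable patient normally attended it. Section 13.2 keeps vaccinated patients who stop lenalidomide in the Day 43 evaluation, which limits toxicity-driven loss. All of this stands.

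Three stronger readings are tempting, and the documents do not support them.

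- A reader might infer that the rule itself causes the fall in power. The complete-case comparison shows that at 10% equal loss almost all of it is lost information. The calculations also pool Day 15 and Day 43 losses, and only Day 15 losses are recoverable.
- A reader might infer that the rule favors lenalidomide. Nothing in the documents indicates that Arm B would lose more titres; if Arm A loses more, the rule works against lenalidomide. The kit-sheet omission does not depend on arm, so it is no evidence of differential bias.
- A reader might infer that the baseline titre should simply replace a missing Day 15 titre in the primary analysis. The two are not interchangeable. In Arm A the baseline precedes two weeks of lenalidomide, so a rise from baseline could include a pre-vaccine drug effect in that arm only. The draw may be up to 14 days before registration and treatment may start up to 21 days after it (Sections 4.0 and 6.17), so baseline can precede vaccination by about 14 + 21 + 14 = 49 days.

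What the objection does not answer is the comparison under unequal loss: a rule that is the same in both arms still shifts the difference when the losses are not.

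**Conclusion.** The concern holds in a limited form. Missing-as-failure is not reliably conservative for the between-arm comparison. Under assumed losses of 5% and 15%, the go probability with no true effect moves from 0.168 to 0.227 or 0.127, depending on which arm loses more. These figures rest on true rates of 22%, on missingness unrelated to response, and on loss rates that the plan does not supply. They show sensitivity and do not forecast bias.

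Two textual faults stand without any assumption. Appendix VI conflicts with Sections 4.0 and 14.1 on the Day 15 serum. The wording of 16.311 can also mean lacking either titre or lacking both; on the second reading, a patient missing only Day 15 has no stated outcome.

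The Day 15 anchor is a deliberate and defensible choice, and nothing here requires abandoning it. What is missing is a prespecified way to show whether the verdict depends on the missing titres.

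**What to change.** 1. Correct Appendix VI so that the serum tubes are also drawn at Day 15, as Sections 4.0 and 14.1 require.
2. State in 16.311 whether the rule applies when either titre is missing or only when both are.
3. Keep the Day 15 anchored analysis as primary. Prespecify a sensitivity z-test that takes the baseline titre as the pre-vaccine value when Day 15 is missing or unusable. Apply it identically in both arms and flag the patients concerned, because the Arm A baseline precedes lenalidomide.
4. Report missing titres by arm and visit. Repeat the z-test with the remaining missing Arm B titres counted as responses, labelled as a worst-case bound. State that the primary verdict governs, and report whether it is robust to both tests.

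The cost is a corrected kit sheet, a few lines in Section 16, and slightly more analysis of serum that is already mandatory. The worst-case bound is severe, as step 5 of the working shows, so failing it should be read as a limit on robustness and should not overturn a go verdict.
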